2.2 SUBJECTS

2.2.1 Number of Subjects

A total of 36 subjects will be treated on the study at 2 investigational sites in US.

2.2.2 Diagnosis and Main Criteria for Inclusion

Adult subjects with up to 4 DPN Target Lesions with FST 5 or 6.

2.2.3 Study Population Characteristics

Subjects with a clinical diagnosis of DPN who meet all the inclusion criteria and none of the exclusion criteria will be eligible to enroll/randomize in the study. Detailed inclusion and exclusion criteria, see protocol sections 5.1 and 5.2.

2.2.4 Replacement Subjects

If a subject is enrolled to the study but does not receive a dose of study drug, then the subject will be replaced.

2.3 TREATMENT AND RANDOMIZATION

2.3.1 Study Medications, Treatment, and Mode of Administration

A-101 Solution 40% is hydrogen peroxide that will be supplied in a glass ampule with an applicator to be applied to a DPN lesion.

2.3.2 Randomization

Cohort 1 of this study is an open label study. Subject randomization is not applicable for this part of the study.

Subjects that are determined to be eligible for treatment in Cohort 2 will be randomized in a 1:2 ratio to one of the following treatment arms.

- ARM A: A-101 40% Solution; No medical abrasion to the Target DPN Lesions Treatment Days 1, 15 and 29
- ARM B: A-101 40% Solution applied after medically abrading the Target DPN Lesions; Treatment Days 1, 15 and 29

2.3.3 Administration of Treatment

The study medications are for external, topical use on the DPN Target Lesions on the appropriate study subject only.

The treating investigator performing the study medication treatments must comply with the study medication handling warnings. In cohort 1, the treating physician will apply the A-101 Solution 40% to each DPN Target Lesion at Visit 2 and at Visit 4, if applicable.

At Visit 4, any Target Lesion that has a Physician DPN Lesion Assessment grade of >0 and ONLY DPN Target Lesions that have a Physician DPN Lesion Assessment grade of >0, must receive study medication treatment UNLESS either of the following criteria apply to the DPN Target Lesion:

- The DPN Target Lesion has a Visit 4 pre-treatment LSR grade of 3 (severe) for any sign or symptom AND the grade has increased compared to the Visit 3
- The DPN Target Lesion is, in the investigator's opinion, not appropriate for a retreatment (the investigator must note the reason on the subject's Comments CRF page).

In cohort 2, for those subjects randomized to ARM B, the treating physician will medically abrade the Target DPN Lesion prior to apply the A-101 study medication. All subjects in cohort 2 will be allowed to have up to 3 treatment applications of the A-101 study medication. If subjects meet the criteria as outlined above, subjects in cohort 2 may receive 2 additional study medication applications at Visit 3 (Day 15) and Visit 5 (Day 29).

2.3.4 Duration of Treatment

The duration of the study participation is anticipated to be a maximum of 127 days per subject. The final visit (Visit 8), has a maximum allowable visit window of 7 days.

2.4 ASSESSMENTS

2.4.1 Evaluators

The investigator, a designated and appropriately trained staff member (e.g., sub investigator) or the subject will perform the study assessments according to the defined schedules.

2.4.2 Evaluations – Efficacy

2.4.2.1 Physician's DPN Lesion Assessment

The Physician's DPN Lesion Assessment is the investigator's assessment of the severity of the Target DPN Lesion at a particular time point. The investigator should NOT refer to any other assessments to assist with these assessments.

At Visits 1, 2, 3 (cohort 2 ONLY), 4 (cohort 1 ONLY), 5 (cohort 2 ONLY), 6, 7 and 8, the investigator will assess the Target DPN Lesion using the scale below and report the one integer that best describes the severity of the Target DPN Lesion. At Visit 2, and if appropriate at Visit 4 for cohort 1 subjects or Visit 3 and Visit 5 for cohort 2 subjects, the investigator must complete the Physician's DPN Lesion Assessment prior to the study medication treatment.

Table 3: Physician's DPN Lesion Assessment Definitions

Grade	Descriptor
0	Clear: no visible DPN lesion;
1	Near Clear: a slightly visible DPN lesion; lesion may be macular
2	Small: a visible DPN lesion with a diameter of less than 3 mm
3	Large: a visible DPN lesion that is elevated with a diameter of $\geq 3 \text{ mm}$

At Visit 1 and Visit 2, for the subject to be eligible for enrollment to the study the identified DPN lesions must have a Physician's Lesion Assessment of grade ≥ 2 .

2.4.2.2 Lesion Dimensions

At Visit 1 and at Visit 2 prior to enrollment the investigator will be required to measure the diameter and thickness of each Target DPN Lesion. For subjects enrolled to cohort 1 the investigator will measure the diameter of each Target DPN Lesion using the ruler at Visit 4 (prior to retreatment, if applicable), Visit 6, Visit 7 and Visit 8. For subjects randomized to cohort 2, the investigator will measure the diameter of each Target DPN Lesion at Visit 3 (prior to retreatment if applicable), Visit 4, Visit 5 (prior to retreatment if applicable) Visit 6, Visit 7 and Visit 8.

At Visit 1 for the subject to be enrolled and at Visit 2 for the subject to be enrolled each Target DPN Lesion must have:

- A diameter that is between 2 mm and less than 5 mm.
- A height or thickness that is ≤ 2 mm.

2.4.2.3 Subject Self-assessment Scale

For subjects enrolled to cohort 1, each subject will use the Subject Self-Assessment Scale to assess each Target DPN Lesions at the following visits: Visit 1, Visit 2 (prior to treatment), Visit 4 (prior to treatment), Visit 6, Visit 7 and Visit 8. For subjects randomized to cohort 2, each subject will use the Subject Self-Assessment Scale to assess each Target DPN Lesion at the following visits: Visit 1, Visit 2 (prior to treatment), Visit 3 (prior to retreatment, if applicable), Visit 4, Visit 5 (prior to retreatment, if applicable) Visit 6, Visit 7 and Visit 8.

Grade	Descriptor
0	No Visible DPN Lesion
1	Mild; Slightly raised DPN lesion
2	Moderate; Obviously raised DPN lesion
3	Severe; Prominent DPN lesion

Table 4: Subject Self-Assessment Scale

2.4.3 Evaluations – Safety

2.4.3.1 Local Skin Reaction (LSR)

The LSR assessment is the investigator's assessment of the signs and the subject's assessment of the symptoms associated with irritation at each Target DPN Lesion site, which includes the Target DPN Lesion and the area immediately surrounding the Target DPN Lesion.

At Visits 2-8, the investigator and the subject will evaluate the LSR signs and the LSR symptoms at each Target DPN Lesion site respectively.

The investigator will assess the LSR signs as follows:

- Visits 2 and 4 (cohort 1) and Visits 2, 3 and 5 (cohort 2):
 - For each Target DPN Lesion site report the severity for all signs prior to any study medication treatment
 - For every treated Target DPN Lesion site, 20 (±4) minutes after the Treatment Completion Time, report the severity for the following signs:
 - Erythema
 - Edema
 - Scaling/dryness
 - Vesicles/bullae
- Visits 3 and 5-8 (cohort 1) and Visits 4 and 6-8 (cohort 2):
 - For each Target DPN Lesion site, report the severity for all signs.

The subject will assess the LSR symptoms as follows:

• Visits 2 and 4 (cohort 1) and Visits 2, Visit 3 and Visit 5 (cohort 2):

- For each Target DPN Lesion site report the average of the severity over the previous 24 hours for all symptoms prior to any study medication treatment.
- For every treated Target DPN Lesion site, 10 (±4) minutes after the Treatment Completion Time, report the average of the severity of the LSR for all symptoms since completion of the study medication treatment.
- Visits 3 and 5-8 (cohort 1) and Visits 4 and 6-8 (cohort 2):
 - For each Target DPN Lesion site, report the average of the severity over the previous 24 hours for all symptoms.

Both the subject and the study staff member will initial and date the source document to indicate the subject performed the LSR for symptoms as instructed. The staff member must not influence the subject's assessment.

The investigator should report the one integer that best describes the severity of each LSR sign for each Target Lesion site using the scale below. Each subject should report the one integer that best describes the severity of each LSR symptom for each Target Lesion site using the scale below:

Table 5: Grading of Local Skin Reactions

Grade	Descriptor
0	None
1	Mild
2	Moderate
3	Severe

2.4.3.2 Adverse Events

Non-serious AEs will be recorded starting with the subject's first study medication treatment at Visit 2 and continuing through Visit 6. All SAEs regardless of relationship to study medication will be collected and reported from the time the Informed Consent is signed through Visit 6.

2.4.3.3 Laboratory Sampling

Non-fasting blood samples for clinical laboratory analysis will be collected by a qualified staff member at Visit 1 and at Visit 8. Approximately 7.5 mL of blood will be collected for each chemistry sample and 3ml of blood will be collected for the complete blood count (CBC). These blood samples will be sent to a central laboratory for analysis. Refer to the study specific laboratory manual for instructions regarding handling of the blood samples and shipping instructions.

Laboratory tests (minimum) are as follows:

Page **18** of **26** Date: 19-February-2019

Chemistry	Hematology
Albumin	Hematocrit
Alkaline phosphatase	Hemoglobin
Alanine aminotransferase	Platelet count
Aspartate aminotransferase	Red blood cell morphology
Blood urea nitrogen	Red blood cell count
Bicarbonate	White blood cell count
Calcium	White blood cell differential
Chloride	% & absolute
Creatinine	Basophils
Glucose	Eosinophils
Lactate dehydrogenase	Lymphocytes
Phosphorus	Monocytes
Potassium	Neutrophils
Sodium	
Total bilirubin	
Total protein	
Uric acid	

2.4.3.4 Vital Signs

Vital signs will be measured by a qualified staff member at Visit 1, Visit 2 prior to randomization, Visit 4 (cohort 1 ONLY) prior to treatment and at Visit 8. The following items will be measured:

- Body temperature
- Pulse rate
- Respiration rate
- Blood pressure (systolic and diastolic) after the subject sits quietly for at least 5 minutes
- Height (at Visit 1 only)
- Weight (at Visit 1 only)

Any measure that is, in the opinion of the investigator, abnormal AND clinically significant (CS) must be recorded as history if found prior to the first study medication treatment or as an AE if found after the first study medication treatment begins.

A systolic blood pressure >140mm Hg or a diastolic blood pressure >90mm Hg is considered abnormal and therefore must be defined as CS or non-clinically significant (NCS) on the Case Report Forms (CRFs).

2.4.4 Other Evaluations

At Visit 1, the investigator or designee will collect demographic information including date of birth, sex at birth, race, ethnicity, and FST for each subject.

Skin Type Classification	Description
Туре І	Always burns, never tans (pale white; blond or red hair; blue eyes; freckles)
Type II	Usually burns, tans minimally (white; fair; blond or red hair; blue, green, or hazel eyes)
Type III	Sometimes mild burn, tans uniformly (cream white; fair with any hair or eye color)
Type IV	Burns minimally, always tans well (moderate brown)
Type V	Very rarely burns, tans very easily (dark brown)
Type VI	Never burns, never tans (deeply pigmented dark brown to darkest brown)

 Table 6: Fitzpatrick Skin Type (FST) Scoring System

3 STATISTICAL METHODOLOGY

This plan describes methods planned for the analysis and display of efficacy and safety endpoints. Summaries will be based on mainly descriptive summaries for each assessment.

3.1 GENERAL STATISICAL CONSIDERATIONS

Descriptive statistics (mean, standard deviation [Std Dev], median, minimum [Min], and maximum [Max]) will be used for continuous variables; number and percentage of subjects will be used for discrete variables. In general, the last measurement prior to the first dose of study treatment will be used as the baseline value. Nominal visits will be used for by-visit summaries and analyses.

All treatment group comparisons will be made at the 0.05 level using a two-sided hypothesis test, unless otherwise specified.

Summaries will be presented by each arm, ie, Cohort 1 FST 5, Cohort 1 FST 6, Cohort 2 Arm A, Cohort 2 Arm B, and Total (combining both cohorts subjects).

All tabulations of summary statistics, graphical presentations, and statistical analyses will be performed using SAS[®] Version 9.2 or higher.

3.2 ANALYSIS POPULATION AND DISPOSITION OF SUBJECTS

3.2.1 Data Sets Analyzed

Per-protocol (PP) analysis set

All treated subjects completing all treatment visits and Visit 8 with no major protocol violations.

Intent-to-Treat (ITT) analysis set

Intent-to-Treat (ITT) analysis set includes all treated subjects with at least one post-baseline visit.

Safety analysis set

The Safety Analysis Set includes all treated subjects.

3.2.2 Disposition of Subjects

The numbers of subjects screened (ie, signed informed consent), enrolled/randomized, treated, and discontinued from treatment (by reason), will be summarized for each cohort separately.

3.3 DEMOGRAPHIC AND OTHER BASELINE CHARACTERISTICS

Demographic and baseline characteristics will be summarized for the PP and Safety analysis sets. Gender, race, ethnicity, and FST will be summarized with number and percentage presented for each category. Age, height, weight will be described with summary statistics (n, mean, Std Dev, median, minimum, and maximum).

3.4 MEDICAL HISTORY

Medical history will be summarized by body system class using the Safety analysis sets.

3.5 PRIOR/CONCOMITANT MEDICATIONS

The number and percentage of prior medications, and concomitant medications will be summarized by Antomical Therapeutic Chemical (ATC) and preferred term (PT) separately using Safety analysis set.

Medications taken any time prior to the first study treatment are counted as prior medications. Those taken any time on or after the first application of study medication through 30 days after the last application of study are counted as concomitant.

Subject will be counted only once within each classification. The same subject may contribute to two or more preferred terms within the same ATC classification.

3.6 EFFICACY ANALYSIS

All efficacy analyses and summaries will be performed on the PP analysis population by randomized treatment group. The primary efficacy analysis will be repeated on the ITT population.

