3.6.1 Physician's Leasion Assessment (PLA) Analyses

PLA related parameters will be summarized at lesion level and at subject level.

At each visit or applicable visit, the following analyses will be performed:

• Descriptive statistics will be provided for the per-subject mean change from baseline in PLA for each post-baseline scheduled visit separately for the PP population.

- Descriptive statistics will be provided for the per-subject mean change from baseline in PLA for each post-baseline scheduled visit separately for the ITT population.
- The number and percent of subjects having all lesions with PLA score of 0 will be provided for each post-baseline scheduled visit separately (PP population).
- The number and percent of subjects having all lesions with PLA score <= 1 will be provided for each post-baseline scheduled visit separately (PP population).

The following treatment group comparisons will be performed for PLA endpoints from Cohort 2:

- Tretment group comparisons will be made for the change from baseline in per-subject mean PLA score at each post-baseline scheduled visit for the PP population. These comparisons will be made using a repeated measures mixed model where treatment group and time (visit) are included as class variables and baseline per-stubject mean PLA score and number of treated lesions will be included as continuous covariates. The per-subject PLA measures over time will be treated as repeated measures by including subject as a random effect. An unstructured variance covariance matrix will be assumed. If the model experiences convergence issues with the unstructured variance covariance assumption, then a compound symmetric assumption will be used. The difference in least square means for the treatment groups along with corresponding 95% confidence intervals and p-values will be provided for each of the scheduled visits. A plot of the treatment group least square means (and 95% confidence intervals) across time (visit) will be provided.
- Tretment group comparisons will be made for the change from baseline in per-subject mean PLA score at each post-baseline scheduled visit for the ITT population using LOCF for missing data. The model for analysis and output will match that of the PP population analysis and output described above.

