- A logistic regression will be used to make treatment comparions in the proportion of subjects having all lesions with PLA score of 0 (PP population). This analysis will be performed at each scheduled visit separately. This model will include a class variable for treatment group as well as baseline per-subject mean PLA score and number of treated lesions as a continuous covariate. Model based odds ratios, corresponding 95% confidence intervals and p-values will be provided at each scheduled visit.
- Similarly, a logistic regression will be used to make treatment comparions in the proportion of subjects having all lesions with PLA score of <= 1. This model and output will be the same as described for the PLA score = 0 analysis.

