4 CHANGES TO PLANNED ANALYSES

After communications with the FDA, the sponsor is no longer persuing a separate indication for in patients with DPN. Therefore, an abbreviated report will be produced for A-101-DPN-201. This abbreviated report will contain all the safety of a full report, but only the primary and key secondary efficacy analyses will be reported. As a result, the following descriptive statistics mentioned in the protocol will not be produced:

- Number and percentage of lesions by PLA score categories (clear, near-clear, small, and large): overall, separately for face or neck target lesions, separately for subjects with FST 5 and 6;
- Summary statistics on PLA score (mean of all lesions): overall and separately for subjects with FST 5 and 6;
- Summary statistics on percentage of lesions that are clear (PLA=0): overall, separately for face or neck target lesions, separately for subjects with FST 5 and 6;
- Summary statistics on percentage of lesions that are clear or near clear (PLA=0 or 1): overall, separately for face or neck target lesions, separately for subjects with FST 5 and 6;
- Number and percentage of lesions by location (face, or neck): overall and separately for subjects with FST 5 and 6.

Furthermore, the following hypothesis tests will not be performed:

- Change in percentage of lesions that are clear (PLA=0) from baseline evaluation to the last evaluation of the lesions ANCOVA model;
- Change in percent of lesions that are clear (PLA=0) or near-clear (PLA=1) from baseline evaluation to the last evaluation of the lesions ANCOVA model;
- Change in longest lesion diameter from baseline to the last lesion measurement ANCOVA model;

The protocol also states that efficacy summaries may be presented for the intent-to-treat (ITT) population using LOCF to impute missing data. The primary endpoint will be summarized and analyzed for the ITT population using LOCF to impute missing data, but none of the other efficacy endpoints will be summarized or analyzed for the ITT population.

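### As written, the Cohort 2 PLA model cannot give per-visit treatment differences and the AE overview omits treated subjects with no later visit; leading with all observed PLA data would be a cheap, modest gain

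*SAP*

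**What the plan says.** - **Efficacy set.** SAP 3.6: "All efficacy analyses and summaries will be performed on the PP analysis population by randomized treatment group". SAP 3.2.1 defines PP as "All treated subjects completing all treatment visits and Visit 8 with no major protocol violations". Protocol 12.2 also leads with PP.
- **ITT set.** SAP 3.2.1: "Intent-to-Treat (ITT) analysis set includes all treated subjects with at least one post-baseline visit". The Safety set in the same section is simply everyone treated.
- **Lead model.** SAP 3.6.1 specifies a repeated measures mixed model in which "treatment group and time (visit) are included as class variables", with baseline mean PLA and number of treated lesions as covariates. Covariance is unstructured, with compound symmetry as the fallback. The output is a difference in least square means, with confidence interval and p-value, for each scheduled visit, plus a plot over time.
- **ITT repeat.** The same model is fitted at each "post-baseline scheduled visit for the ITT population using LOCF for missing data". SAP section 4 says that no other efficacy endpoint gets an ITT analysis.
- **Timing of scores.** At treatment visits the investigator completes the "DPN Lesion Assessment prior to the study medication treatment" (SAP 2.4.2.1). For Cohort 2 these include Visits 3 and 5.
- **Safety.** SAP 3.7 makes the Safety set the default but allows exceptions. SAP 3.7.3 makes one, putting the AE overview on ITT. Protocol 12.4 names the ITT population in one paragraph and all treated subjects in the next.

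**The concern.** Three separate matters meet here.

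First, the model terms do not deliver the promised output. This does not depend on dropout, and it affects the lead analysis, its ITT repeat and the plot.

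Second, the AE overview counts TEAEs that lead to discontinuation. A subject treated at Visit 2 who reacts and never returns is in the Safety set but not in ITT. The overview could then show fewer such subjects than the tables beside it. The abbreviated report keeps all safety output, so this would appear in it.

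Third, PP selects subjects after randomisation, in an open-label trial with an investigator-scored endpoint. A mixed model can use the visits a non-completer did attend. PP drops those subjects, and LOCF replaces their gaps with single values. In Cohort 2 the value carried to Day 106 can be one scored before the second or third application.

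**Working it through.** The plan states no power, effect size, SD or dropout rate, so there is no figure of its own to reproduce.

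**1. Model terms.** As listed, the expected change for subject *i* at visit *j* is

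μ + α·arm + β_j + γ·baseline + δ·lesions.

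The Arm B minus Arm A difference at visit *j* is α for every *j*, whatever the covariance structure and even with complete data. A trial fit on simulated data (8 and 16 subjects, six visits) gave one estimate repeated without the interaction and six different estimates with it. Adding θ_j·arm makes the difference α + θ_j and costs (number of visits − 1) parameters. The procedure table for Cohort 2 (protocol Table 3, SAP Table 2) schedules PLA at Visits 3 to 8: six visits, five parameters. Protocol 8.1.2 and SAP 2.4.2.1 limit Visit 4 PLA to Cohort 1: five visits, four parameters.

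**2. AE overview.** Allocation 1:2 of 24 gives 8 in Arm A and 16 in Arm B. One treated subject with an AE and no later visit changes the overview from 1/16 to 0/15 in Arm B, or from 1/8 to 0/7 in Arm A.

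**3. How likely is a loss?** Protocol Table 1 (same product, seborrheic keratosis):
- Enrolled: 35+172+119+450+487+147 = 1,410. Completed: 34+169+116+446+479+139 = 1,383. Loss: 27/1,410 = 1.9%.
- Highest: 8/147 = 5.4%, in the only open-label study.
- P(at least one of 24) = 1 − (1 − 0.019)^24 = 37%, or 1 − (1 − 0.054)^24 = 74%.

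This counts departure at any time. PP can also lose subjects through missed treatment visits and major violations, for which the documents give no rate.

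**4. How large is the shift from one early leaver?** Assumed, not from the documents: departure just after Day 15, no true difference, SD 0.7 grade, correlation ρ of Day 15 with Day 106 of 0.2 to 0.7, mean gain from Day 15 to Day 106 of 0.5 to 1.0 grade. The expected maximum of n standard normals, E, is 1.424 for n = 8 and 1.766 for n = 16. Positive means that the leaver's arm looks worse.
- PP, worst or best Day 15 responder leaves: size ρ × 0.7 × E/(n − 1). A random leaver gives 0. If the worst leaves, that arm looks better.
- LOCF: (1/n) × [gain ± 0.7 × E × (1 − ρ)], plus for the worst responder, minus for the best, gain/n if random.

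| Leaver | Arm A (n = 8) | Arm B (n = 16) |
|---|---|---|
| PP, worst or best (size) | 0.03 to 0.10 | 0.02 to 0.06 |
| LOCF, random | +0.06 to +0.125 | +0.03 to +0.06 |
| LOCF, worst | +0.10 to +0.22 | +0.05 to +0.12 |
| LOCF, best | −0.04 to +0.09 | −0.03 to +0.04 |

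Standard error of the difference: 0.7 × √(1/8 + 1/16) = 0.303. Every shift is smaller.

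**5. Does the observed-data model do better?** In simulation (six visits, treatment-by-visit means, gain 1.0, continuous scores):
- Departure random or driven by the Day 15 score: largest shift 0.005 with unstructured covariance.
- Compound-symmetric fallback when the true correlation decays over visits: up to about 0.03 (Arm B) or 0.04 (Arm A).
- Departure driven by the worst unrecorded Day 106 value: observed-data model 0.03 to 0.08 (Arm B) and 0.06 to 0.14 (Arm A); LOCF 0.00 to 0.04 and 0.02 to 0.09.

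**The case against.** The choices are prespecified and disclosed. Protocol 12.2 leads with PP and makes the ITT/LOCF summaries optional; the SAP makes the repeat definite for the primary endpoint, and section 4 says that the rest is PP only. The trial has no power basis (protocol 12.1), its summaries are mainly descriptive (SAP 3), and "the sponsor is no longer persuing a separate indication for in patients with DPN". This stands, and it limits the weight of the third matter. It does not repair the first two.

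The size figures pair the chance of any loss with an early departure, when the carried score is oldest. A subject leaving after Visit 6 or 7 would carry a score taken after all treatment visits. That also stands.

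A reader might infer that LOCF always counts against the arm that loses a subject. It does not: that direction comes from the assumed gain after Day 15. With zero gain a random leaver causes no shift, and if scores worsen the sign reverses. Durability of response is itself the secondary objective, so late worsening cannot be ruled out. Nor is the observed-data model better in every case, as step 5 shows.

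On the model, the request for per-visit differences makes the intent clear, so the missing term may be incomplete wording. An analyst following the listed terms would still produce the wrong table.

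On AEs, protocol 5.4 and 10.2.3 require continued monitoring after withdrawal for an AE. That makes a complete absence of later visits less likely, but does not exclude it.

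**Conclusion.** The missing treatment-by-visit term and the AE overview set are wrong as written and should be corrected. The first affects the lead output with certainty if the listed model is fitted. The second affects it only if a treated subject has an AE and no post-baseline visit.

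The PP lead with a LOCF repeat is a weaker choice than the mixed model on observed data, with a small expected effect: at most about 0.12 grade (Arm B) or 0.22 (Arm A) for one early leaver, against a standard error of about 0.30. That rests on the assumed SD, correlation, gain and time of departure, and on treating the score as continuous.

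Two stronger readings are not supported. One is that the planned comparison is biased in a known direction: PP and LOCF can err in opposite directions, and neither sign is fixed by the documents. The other is that adverse events are lost: the subject stays in the safety summaries that use the default set, and only the overview omits them.

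**What to change.** - **SAP 3.6.1:** add a treatment-by-visit term to the mixed model. Reconcile the Cohort 2 procedure tables with protocol 8.1.2 and SAP 2.4.2.1 on whether Cohort 2 has a Visit 4 PLA.
- **SAP 3.7.3:** put the AE overview on the Safety set. Align protocol 12.4, or note the change in SAP section 4.
- **SAP 3.6 and 3.6.1:** lead with the mixed model fitted to all observed post-baseline PLA from randomised and treated Cohort 2 subjects, and state that it is valid under missing-at-random. Keep PP and, if wanted, LOCF as sensitivity analyses. Record the departure from protocol 12.2 in SAP section 4 and amend the LOCF statement there.
- Responder analyses may stay on PP.

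The cost is wording in four places in the SAP, one model term (four or five parameters) and no new data. The downsides are that missing-at-random cannot be checked from the data, and that with 24 subjects the unstructured fit may fail and fall back to compound symmetry.
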